5.1 Ethics

5.1.1 When will obtain consent?

A local researcher will approach all people identified from line lists available from the ongoing study on the prevalence of disability due to leprosy for leprosy ulcers and local health centres. Those with ulcer due to diabetes will be identified from the line list developed from the combined list from the and local health centres. Except those under 18 years of age, all those with neuropathic ulcers will be included in the study – for instance if a person has difficulty in communicating, they will still be offered entry into the study. People who are willing to participate will be given a Patient Information Leaflet (Appendix 1) to read but consent will be sought after the day when this is provided. If a person cannot read, then they will be assisted in understanding the information in the leaflet. The Patient Information Leaflet (Appendix 1) and informed Consent Form (Appendix 2) will be translated into Hindi and Nepali and back translated according to the WHO methodology.(37)

5.1.2 Who will take consent?

One of the local trained researchers deployed on the grant will offer the person participation in the data collection for the study. The researchers will complete GCP training online and will be included in the delegation log. They will be trained to obtain consent as follows: They will attend a 30 minute talk given by the project manager covering the essence of the Helsinki recommendations (1964 and revisions) (38) and the right to withdraw at any stage ([name](India), [name] (Nepal), local or [name](University of Birmingham).

5.1.3 How will we obtain consent?

The forms will be read aloud to people who are illiterate. If they are unable to sign their name using a writing instrument, then they will sign consent by thumb print (or fingerprint if the thumb has been damaged by leprosy). See data management regarding bio-metric data. Screening and the obtaining of informed consent will be evidenced by the completion of an electronic case report form (e-CRF) within the REDCap closed data capture system by staff named on the delegation log. If any person declines to contribute data, then it will be noted that a person has declined but no data will be retained on them. However, reasons for not taking part will be recorded in a place provided on the computer.

5.1.4 Withdrawal

Participants are free to withdraw at any time as explained to people in the information provided. The participant may withdraw in two ways:

- 1. Does not wish to continue in the intervention, but happy to contribute follow-up data
- 2. Does not wish to continue to contribute follow-up data

There will be a notice of withdrawal form on the data collection tablet for people in the second group above but people who are in the first group will continue to contribute data but their withdrawal from participation in group activity will be noted.

As this is a feasibility plus trial, there will be no data monitoring committee and no interim analysis. Rather, the study managers will monitor accruing data as a check on quality and so that action may be taken if data are incomplete.

5.2 Protocol amendment

Any protocol amendment will be reported to the Leprosy Mission Trust India and Nepal Health Research Council (NHRC) ethics committee to approve the change.

5.3 Sponsorship

The Leprosy Mission Trust India will be the sponsor.

5.4 Data collection, use and storage

We will adhere to international standards on conducting health research (39). We will ensure that the communities taking part in this research are also those who will see the benefits, and that the privacy of participants are protected. All data (save consent forms) will be collected using tablets (which will also be used to take photographs). Patient facing materials (Information/consent forms) will be translated and back translated according to WHO criteria (e.g. back translation carried out independently of forward translation and results checked independently). Data will be captured and encrypted using the REDCap database at The George institute for Global Health India. We will comply with local regulations governing research:

https://intranet.birmingham.ac.uk/it/documents/public/Information-Security-Policy.pdf and the Indian Council of Medical Research.

All data generated from this study will be classified according to the University of Birmingham Information Security Framework. All data will be collected and stored electronically to eliminate data collection errors, such as contradicting answers, building on our experience under our current NIHR Global Health Research Unit on Improving Health in Slums. Data will be reported on an electronic Case Report Form (eCRF), and all local research staff will be trained to collect data directly onto electronic tablets. Data will be acquired and stored on the REDCap platform with access restricted by passwords at the local site in India and Nepal. Each participant will be allocated a unique study number when they agree to participate which will be used on all documents. REDCap is capable of storing and transferring photographic images.

Range limits and logic checks (e.g., for conflicting responses) will be built into the REDCap form to prevent erroneous data entry. Base-line data from the first ten patients will be cross-checked by the local lead investigator to assure that full and accurate data are collected.

All data will be stored only in backed-up shared network spaces. "Restricted" and "reserved" data files will be encrypted using PGP encryption. The study site in India will create their own unique set of PGP keys to access data locally. For data transmission between study sites and the University of Birmingham the files will be encrypted using the relevant study site public key. Only authorised individuals at each institution will have access to the data. The information collected on REDCap is encrypted on the tablet and sent through a secure link to the server hosted at the George Institute for Global Health.

Once the project has ended, the anonymised trial data will be made available for sharing with all requests being approved by the Chief Investigator. Those accessing the data will abide by the same rules as are applicable throughout the project. Data will be stored for a minimum period of ten years and then reassessed rather than destroyed, as per the local data management policy. During the 10-year post-project period paper data, such as consent forms, will be archived locally in India and Nepal in locked cabinets. Electronic data including photos will be stored in an encrypted archive at the George institute for Global Health India. All electronic data held locally at the investigator site in India will be archived for ten years and then deleted. Should the investigator site wish to access the electronic data, this will be done through the local secure file transfer portal.

5.5 Study organization and management

5.5.1 Study management group

The Study Management Group (SMG) includes individuals at the University of Birmingham, The Leprosy Mission Trust India and The Leprosy Mission Nepal who are responsible for the day-to-day management of the trial. This will include the Chief Investigator for the whole study ([name]), local Investigator in India ([name]) and Co-Principal Investigator ([name]), local Investigator in Nepal ([name]), Project Manager ([name]) for overall study and local Project Manager, lead methodologists and patient representatives. The Study Management Group will meet monthly by teleconference, but this may be more frequent if deemed necessary by the members. The role of the Study Management Group is to monitor all aspects of the conduct and progress of the trial, ensure that the protocol is adhered to and take appropriate action to safeguard participants and the quality of the trial itself.

5.5.2 Monitoring and oversight

The trial will be overseen by the clinical trials unit at George Institute for Global Health. They will provide overall supervision of the trial and will ensure that it is conducted in accordance with the principles of

good clinical practice and relevant regulations. They will review the safety and efficacy data during the active phase of the trial handbill advice on the continued recruitment of trial participants. They will meet by teleconference and the team will consist of a trial manager, statistician and data manager.

5.2.3 Summary of staff training

All current site staff in India and Nepal have undertaken Good Clinical Practice Training and new appointees to the trial will be required to complete online training. Staff will be trained to seek patient consent (as outlined in 5.1.2).

5.6 Dissemination and Publication

The results of the study will be reported to collaborators of this study. Equal credit will be given to those who have collaborated in the trial.

The findings will be shared with the patients and communities through the networks of The Leprosy Mission Trust India and The Leprosy Mission Nepal who have extensive experience in working with the patient communities. We shall also present our work at local and international conferences.

Tools we will use to disseminate our research output include: bite-sized research reports in lay format; publication in peer reviewed international journals; public announcements in LMICs; policy briefings; print and online media; the director's news blog (680+ subscribers); institutional and social media accounts and websites.

5.7 Gantt Chart

	Apr	May	Jun	Jul	Aug	Sep	Oct	Nov	Dec	Jan	Feb	Mar	Apr	May	Jun	Jul	Aug	Sep	Oct	Nov
Ethics Approval																				
Recruitment of staff																				
Training of staff																				
Line listing & tracing																				
(DM) and leprosy																				
patients																				
Recruitment of																				
patients																				
Intervention																				
Follow-up																				
Qualitative interview																				
Data cleaning																				
Analysis																				
Report writing &																				
Publication																				
Contingency																				

Ethics section:

SECTION 2

Risk and	What are the potential risks to the participants? Consider social and emotional
benefits	risks as well as more obvious physical risks.
Schents	There are no additional risk associated with participating in the study. The treatment
	method of removable walker works the same way as total contact cast which has
	been in practice for ulcer care in leprosy. Patients may develop skin abrasion due to
	ill-fitting walker boots. However, removable walkers used in this study is considered
	safe as it comes with soft inner lining to prevent skin abrasions. We expect that
	application of removable cast in the community will help ulcer heal faster without
	requiring for hospital admission.
	What is your risk management plan?
	If patient develops skin abrasions, we will discontinue the removable walker boot
	and patient will be called to hospital for medical care which will be as per standard
	protocol of the Leprosy Mission Trust India hospital in Champa.
	What will be the companyation for unexpected risks?
	There are no compensation planned for expected risks
	There are no compensation planned for expected fisks.
	What are the potential benefits to the participants?
	In routine care micro-cellular rubber footwear is provided for patients with
	insensitive foot irrespective of presence of ulcer. The treatment provided in this
	study are standard care for ulcer management in leprosy. Regular monitoring of
	ulcers and feedback to patient will help in healing of ulcers.
Safety and	Does this study involve invasive or hazardous procedures, ionizing radiation or
other	hazardous substances (including radiological imaging, vein puncture, or intimate
	physical examination)?
controls	
	No
Informed	What will be the procedure for seeking informed consent from research
consent	participants? How will "research", "randomization", "risks and benefits" be explained?
	Potential study participants will be provided with the printed information sheet (see
	appendix 1). Adequate time will be given for patient to read and take decision. In
	case patient is unable to read, project staff will read and explain to the patient. The
	decision to participate in the study will voluntary.
	What will be the procedure for seeking informed consent from parents/guardians
	etc of research participants who are children, mentally/physically challenged? How
	will assent be obtained from these research participants?
	Children less than 18 and those with mental health issues will be excluded from the
	study as they will not be able to follow the instructions and keep the removable
	walker boot on for the required period.

	How will it be made clear that participants are under no compulsion to participate and may withdraw at any time without jeopardizing any service delivery or their relationship with the researcher?
	Decision to participate in the study is completely voluntary. Point of entry into study is when patient presents with non-infected ulcer. If patient decides not to join the study, they will continue to get the routine care without any compromise (self-care & Micro-cellular rubber footwear) for their insensitive feet and ulcer as per standard practice.
	Provide a copy of plain language statement and informed consent form in English and local language.
	Patient information sheet and informed consent is provide in the Appendix 1 and 2. It has been translated into Hindi which will be given to study participants.
	Details of proposed compensation and reimbursement of incidental expenses.
	No compensation and reimbursement will be provided.
	Statement of probable ethical issues and steps taken to tackle the same.
	We do not envisage any specific ethics issues at this stage. If any issues arise during the study will be brought to the ethics committee for the approval.
Potential conflict of	None.
interest	

Confidentiality, ownership and storage of data and dissemination plans					
Confidentiality					
The raw data collected will be locked and protected	Agree				
The electronic data will be pass-word protected	Agree				
Ownership and storage of data					
The data collected during the research will be stored and maintained by	Agree				
TLMTI principal investigator. The other principal investigators will have a					
copy of the data					
All the principal investigators will be responsible for the safety of the data.	Agree				
The data collected will be an intellectual property of TLMTI and it should be	Agree				
submitted to TLMTI after submission of thesis/publications					
Publication plans					
All the principal investigators with mutual agreement will publish articles /	Agree				
reports					

V 0.7

TLMTI will be acknowledged appropriately in thesis/publications from the	Agree					
study						
Potential conflict of interest:						
None:						
Dissemination of research findings						
How will the results be disseminated?						
The results of the study will be reported to collaborators of this study. Equal credit will be given to						
those who have collaborated in the trial.						
What information will be fed back to the participants and/or participating organization?						
The findings will be shared with the patients and communities through the networks of The						
Leprosy Mission Trust India and The Leprosy Mission Nepal. Both the organization have an						
extensive experience in working with the patient communities. We shall also present our work at						
local and international conferences.						

6. Appendix

6.3 Appendix 3: Data collection form

Case / Patient record form (CRF)

A. Demographic data

- 1. Patient ID (study number):
- 2. Randomization number:
- 3. Group: Intervention / Control
- 4. Age: In years
- 5. Gender: Male / Female / Third gender
- 6. Village/Area name:
- 7. Block:
- 8. Residence: Rural / Urban
- 9. Height in cm:
- 10. Weight in kilograms:
- 11. Education level (number of years of education completed):
- 12. Employment: Farming / Employed / self-employed or own business / labourer / student / house wife / unemployed / unable to work due to disability
- 13. Family Income per month in INR:
- 14. Marital status: Single / Married / divorced / widowed
- B. Clinical data

Leprosy only

- 15. Duration of leprosy in months:
- 16. Sensory loss (unable to feel 10 grams of monofilament): Yes / No
- 17. Sensory loss: Right / Left / Both
- 18. Duration of foot impairment in months:
- 19. EHF score (for leprosy only): Foot (EHF) score:

Diabetes only

- 20. Type of diabetes: Type I / Type II
- 21. Duration of diabetes in months:
- 22. Glycaemic control:

23. Dorsalis Pedis Pulse:

Limb details (information about the foot in which the index ulcer is present)

- 24. History of previous ulceration: Yes / No
- 25. History of previous amputation (minor such as toe): Yes / No
- 26. Sub-talar alignment: Neutral / Supinated / Pronated
- 27. Claw toes: Yes / No

Ulcer details

- 28. Number of active ulcers:
- 29. Location of index ulcer: right foot / left foot
- 30. Site of the index ulcer: fore foot / mid foot / heel
- 31. Ulcer recurrence: First / second / third / fourth / fifth / more than five times
- 32. Duration of the Index ulcer in months:
- 33. Presence of infection in the index ulcer: Present / Absent
- 34. Exudate in the index ulcer: None / Mild / Moderate / Copious
- 35. Photograph taken: Yes / No
- 36. Ulcer metrics baseline: Length in cm:
- 37. Ulcer metrics baseline: Width in cm:
- 38. Co-morbidities: Yes / No If Yes, specify:

Pedometer recordings:

Variable	1 st week	2 nd week	3 rd week	4 th week	5 th week	6 th week	7 th week	8 th week
Date								
Pedo. – 1								
(Off-								
loading								
device)								
Pedo. – 2								
(in hand)								

Follow-up assessment

39. Ulcer metrics during follow-up:

				At 8 th week		
	A+ 2nd weak	At ath	At Cth wook	Or		
	ALZ WEEK	AL4 WEEK	ALD WEEK	At complete		
				healing of ulcer		
Date						
Photograph taken	Y/N	Y/N	Y/N	Y/N		
Length in cm						
Width in cm						
Adverse events	V /N	V /N	V /N	V /N		
related to ulcer	t/IN	t/IN	t/IN	t/IN		
If yes, specify						
Adverse events	V /N	V /N	V/N	V /N		
related to device	t/IN	T/IN	1/11	T/IN		
If yes, specify						

User satisfaction with off-loading devices

(at completion of 8 weeks or complete healing of ulcer)

Quebec User Evaluation of Satisfaction with Assistive Technology (QUEST) 2.0

1	2	3	4	4		5			
not satisfied at all	not very satisfied	more or less satisfied	quite sati	quite satisfied			very satisfied		
How satisfied a	ASSISTIVE DEVICE								
1, the dimension	ns (size, height, l	ength, width) of	vour						
assistive device	?		,						
Comments:				1	2	3	4	5	
2. the weight of	your assistive de	evice?							
Comments:	-			1	2	3	4	5	
3. the ease in ad	ljusting (fixing,	fastening) the par	rts of						
your assistive de	evice?								
Comments:				1	2	3	4	5	
4. how safe and	secure your ass	istive device is?							
Comments:				1	2	3	4	5	
5. the durability	y (endurance, res	istance to wear) o	of your						
assistive device?	?								
Comments:				1	2	3	4	5	
6. how easy it is	to use your assis	stive device?							
Comments:				1	2	3	4	5	
7. how comfort	able your assistiv	ve device is?							
Comments:				1	2	3	4	5	
8. how effective	your assistive d	evice is (the degr	ee to						
which your devi	ce meets your ne	eds)?							
Comments:				1	2	3	4	5	

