4.6.3 Randomization and allocation

Participants will be enrolled sequentially, and randomly allocated (1:1) to receive removable walker boot or MCR using the "digital sealed envelope" method resident in a computer. An allocation table will be generated remotely by the trial statistician at the George Institute of Global Health India. A permuted block random method will be used to generate the randomization sequence within each stratum.

Randomly selected blocks of size 2, 4, 6, or 8 will be generated to maintain balance between the numbers allocated to each of the two groups and to ensure allocation concealment. The generated table will be uploaded into the REDCap software to be used for participant enrolment. Access to the allocation table will be restricted. Trial staff in India and Nepal will not have access to the allocation table. When a participant's details are submitted, the trial arm and a unique study number will be assigned and revealed to the local clinician so that the randomized group that the participant is assigned to cannot be

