4.6.5 Main outcome measures

- 1. Adherence to removable walker boot: Adherence will be measured using pedometer; one placed inside the walker boot and second on patient's wrists as a watch/ in pocket. The pedometer will provide data on number of steps taken by patient during the assessment period which will be recorded weekly. We will compare the groups based on their steps per day. In addition, the difference in cumulative steps recorded between the two pedometers will provide a further measure the compliance to walker boot. We will measure the difference in the difference between intervention and control.
- User satisfaction: We will measure the user satisfaction with the off-loading devices using the Quebec User Evaluation of Satisfaction with Assistive Technology (QUEST) 2.0 at complete healing of ulcer or at 8 weeks from recruitment, whichever is earlier.
- 3. Ulcer healing: We will measure the healing of ulcer time to (complete epithelisation of ulcer) and also measure the rate of healing. All observations will be based on 'blind' assessment. The patient will be followed up for 8 weeks and photographs of ulcers will be taken at baseline and after every 2 weeks until the ulcer heals or at 8 weeks, whichever is earlier, to measure the ulcer area. The ulcer will be measured from the photographs taken using the data collection tablets. The ulcer will

altered.

be measured by masked observers in another site using the PUSH (Pressure Ulcer Scale for Healing) tool with which we have considerable experience.

The photographs of the ulcer will be taken using standard and uniform method in both the study sites. Photographs will be taken in a well-lit area in a long sitting position with the foot elevated slightly on soft material. The image of the ulcer will be captured by the research assistant standing directly in front of the patient with the camera placed parallel to the affected foot/ulcer.

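### Appendix 3 counts active ulcers only at baseline and asks at follow-up only about harms judged related to ulcer or device, so capture of new ulcers and falls is unreliable

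*Protocol*

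**What the plan says.** Protocol section 4.6.4 points to Appendix 3 (section 6.3) for the detailed data collection form. On that form:

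- Item 28, "Number of active ulcers", stands among the baseline ulcer details.
- The follow-up table (item 39) has four columns: week 2, week 4, week 6, and week 8 or healing. Each holds a date, a photograph tick, one length, one width and two adverse-event rows, one for events "related to ulcer" and one for events "related to device". A free-text line opens after a yes.
- Item 3 is "Group: Intervention / Control".

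Under section 4.6.3, "the trial arm and a unique study number will be assigned and revealed to the local clinician". Section 4.6.5 has the follow-up photographs taken "with the camera placed parallel to the affected foot/ulcer".

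On oversight, section 5.1.4 says that "there will be no data monitoring committee and no interim analysis". Section 5.5.2 gives the clinical trials unit the task of reviewing safety data while the trial runs and advising on recruitment. Section 5.5.1 asks the management group to "take appropriate action to safeguard participants and the quality of the trial itself".

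**The concern.** Relatedness is a judgement made after an event is noticed. Here it decides whether the event is written down at all. If someone develops an ulcer on the other foot, or falls, and the assessor thinks neither the ulcer nor the device was responsible, both rows are correctly answered No and no trace remains on the form. The protocol gives no rule for judging relatedness, and the assessor probably knows the arm.

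Two uses of the data are at stake. The first is the safety review in section 5.5.2, which matters more without a data monitoring committee. The second is the pilot purpose. Section 3 makes trying out trial methods and measurements a secondary objective, and sections 1.1 and 2.2 look ahead to a trial of whether the device reduces new ulcers and ulcer complications. The form has no repeatable measure of new ulcers to try out.

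**Working it through.** No sample size, power or error-rate figure bears on this point, and the protocol states no figure to reproduce. The check is a field count on Appendix 3 and a search of the rest of the protocol for another place where such events would be recorded.

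**Field count**

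| Item | Baseline | Follow-up columns (of 4) |
|---|---|---|
| Number of active ulcers | 1 | 0 |
| Adverse-event rows limited to related events | – | 2 rows in each of 4 |
| Adverse-event row regardless of cause | – | 0 |
| Dedicated new-ulcer or fall item | – | 0 |

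- Harm answers per participant: 2 rows × 4 columns = 8 at most, of which 8 depend on relatedness and 0 do not.
- Follow-up columns in the whole trial: 150 participants (section 4.4) × 4 = 600 at most. With 1:1 allocation, 150 / 2 = 75 per arm, so 75 × 4 = 300 per arm at most. The actual number will be lower, because follow-up ends at healing (section 4.7).

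These counts describe the layout of the form. They do not estimate events lost. The protocol gives no rate of new ulcers or falls, and none is assumed here.

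**Other places where an event might be recorded**

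- Section 4.7 lists example complications: a worsening ulcer, abrasions and swelling. The list is open-ended, but it leads to censoring and referral, and it names neither new ulcers nor falls.
- The risk section covers abrasion from the boot: stop the boot and send the patient to hospital. It provides no recording field.
- The photographs centre on the affected foot or ulcer. Sections 1.7 and 4.6.5 speak of ulcers in the plural, so both feet may be photographed when both are ulcerated. Nothing provides for photographing a foot that had no ulcer at entry.
- The satisfaction questionnaire (QUEST 2.0, item 4) has one score, with a comment line, on how safe the device feels, once at the end of follow-up.
- The walking interviews (section 4.8) cover about fifteen patients per site, from the intervention arm only.

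None of these asks every participant in both arms, at each follow-up, whether any event occurred.

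**Are such events foreseeable?** Patients with several or bilateral ulcers are eligible (section 4.4.1). The form allows for sensory loss in both feet (item 17, leprosy patients). The insole moves load from the ulcer to the rest of the foot, and a physiotherapist checks balance when the boot is fitted (both section 4.5.1). These passages do not make new ulcers or falls outcomes of the study, but they show that the events are not far-fetched.

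**The case against.** The strongest reply is that the two rows are broader than they look. Where the form means one particular ulcer it says so, using the term index ulcer in items 29, 30 and 32 to 34. The harm row says only ulcer, so a new plantar ulcer fits it naturally, and a fall in the boot or the footwear fits the device row. Both rows allow a description, and both arms have an off-loading device. This stands: a reader might infer that the form cannot record new ulcers or falls, and the wording does not support that. What remains is an event that staff judge unrelated to either, with no rule to make that judgement consistent.

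Second, care does not depend on these rows. Participants are seen weekly, and complications lead to referral. This also stands, but it concerns treatment of the patient and not the record available for review.

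Third, Appendix 3 is not every form in the study. A withdrawal form and a screening and consent record are mentioned elsewhere, and the electronic build may add fields. That is possible, but the protocol mentions no other harm form.

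Fourth, the protocol never says that reviewers will read No as no event. True. The point is that the form gives them nothing else on which to conclude it.

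Fifth, limiting harms to related events is a defensible choice in an eight-week feasibility study of footwear. Accepted: the protocol contradicts nothing here, and the change is an improvement and not the correction of an error.

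**Conclusion.** The point holds as a minor weakness in data capture. New ulcers and falls can be entered, but only through a judgement of relatedness, and the ulcer count is never repeated. A No in both rows therefore does not establish that neither event occurred. This limits the safety data and the piloting of a new-ulcer measure.

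The size in events is unknown. The field count is certain. The conclusion about safety review assumes that Appendix 3 is substantially the form in use.

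Two stronger readings should be resisted. Because the arm is revealed to the local clinician and appears on the form, a reader might infer that harms will be recorded unevenly between arms. That is possible, but nothing in the protocol shows it. A reader might also infer that the trial's results are compromised. They are not on this account: new ulcers and falls are not outcomes here, and no estimate of adherence, satisfaction or healing is affected.

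**What to change.** In the existing week 2, 4, 6 and 8-or-healing columns of Appendix 3:

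1. Replace the two adverse-event rows with one question: any adverse event (including new ulcer or skin break on either foot, fall, swelling), Y/N, specify. Follow it with separate items on relatedness to the ulcer and to the device.
2. Repeat item 28 in each column, for both feet.

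Each participant would then have up to 4 harm answers given without attribution (1 row × 4 columns) and up to 4 repeat ulcer counts, against none of either now.

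The cost is a minute or two per visit (an estimate), some unrelated events on record, and an amendment notice to the two ethics bodies named in section 5.2 if the form is already approved. No new visit or equipment is needed. The change removes the attribution filter. Assessors who know the arm would still be the ones noticing and reporting events.
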